#### 9.2.5 Composition

For injection: 50 mg, lyophilized powder in single-use vial for reconstitution

#### 9.2.6 Storage Recommendations and Dosage Forms

Two Drug Product (DP) dosage forms are available for MK-3475: a white to off-white lyophilized powder, 50 mg/vial, and a liquid, DP 100 mg/vial, both in Type I glass vials intended for single use only.

- MK-3475) Pembrolizumab Powder for Solution for Infusion, 50 mg/vial (manufactured using the partially formulated DS), is reconstituted with sterile water for injection prior to use. MK-3475 DP is formulated with L-histidine as

buffering agent, polysorbate 80 as surfactant, sucrose as stabilizer/tonicity modifier, and hydrochloric acid (HCl) and/or sodium hydroxide (NaOH) for pH adjustment (if necessary).

- MK-3475) Pembrolizumab Solution for Infusion 100 mg/vial is a liquid DP (manufactured using the fully formulated DS with L-histidine as buffering agent, polysorbate 80 as surfactant, and sucrose as stabilizer/tonicity modifier), and has the identical formulation as that of the reconstituted lyophilized vial.

Both drug product dosage forms are stored under refrigerated conditions (2°C - 8°C). The product after reconstitution with sterile water for injection and the liquid drug product are a clear to opalescent solution which may contain proteinaceous and extraneous particulates. The reconstituted lyophilized product and the liquid product are intended for IV administration. The reconstituted DP solution or the liquid DP can be further diluted with normal saline or 5% dextrose in the concentration range of 1 to 10 mg/mL in IV containers made of polyvinyl chloride (PVC) or non-PVC material. Reconstituted vials should be immediately used to prepare the infusion solution in the IV bag and the infusion solution should be immediately administered. If not used immediately, vials and/or IV bags may be stored at 2-8 °C for up to a cumulative time of 20 hours. If refrigerated, the vials and/or IV bags should be allowed to equilibrate to room temperature prior to subsequent use. MK-3475 solutions may be stored at room temperature for a cumulative time of up to 4 hours. This includes room temperature storage of reconstituted or liquid DP solution in vials, room temperature storage of infusion solution in the IV bag and the duration of infusion. This recommendation is based on up to 24 hours of room temperature and up to 24 hours of refrigerated stability data of diluted pembrolizumab solutions in the IV bags.

#### 9.2.7 Dispensation and Accountability

For this study, pembrolizumab (Keytruda®) will be provided by Merck as Pembrolizumab 50 mg (lyophilized powder for injection) and/or pembrolizumab 100 mg/ 4mL (solution for injection). Please see Appendix K for Preparation and Administration/ Reconstitution of Pembrolizumab (Keytruda®) for Injection (lyophilized powder).

(See also Section 8.5.2 Treatment Dispensation, Compliance and Accountability for Pembrolizumab.)

## 10.0 TREATMENT/ DOSE MODIFICATIONS

### 10.1 Unacceptable Toxicity

Causality for all adverse events should be assessed and if deemed attributable, attempts should be made to attribute to either axitinib, pembrolizumab, or potentially both agents.

In the case of toxicities refractory to routine medical management which are assessed as possibly attributable to both drugs (i.e. liver enzyme elevation, renal dysfunction, thyroid dysfunction, diarrhea/colitis) that may be autoimmune in origin, dose interruption of axitinib should be attempted first. Generally prompt resolution of the toxicity is observed if attributable to axitinib. If the toxicity is persistent, treatment should be administered as per the pembrolizumab treatment guidelines below, including corticosteroid therapy where advised.

Drug-related grade 4 toxicities will generally require subject to discontinue all study treatment. Exceptions include the following: 1) clear evidence that the toxicity was attributable to axitinib alone, resolved upon cessation of axitinib, and there is rationale to continuing pembrolizumab monotherapy 2) Grade 4 lab abnormalities that are not immune-related, where the patient is asymptomatic, and the abnormalities can be reversed with medical treatment. Example: grade 4 hypertriglyceridemia that responds to antilipid drugs. Intolerable grade 2 and grade 3 toxicities should be managed as per dose modification guidelines listed in the tables below. For grade 2 and grade 3 toxicities attributable to axitinib that do not resolve to  $\leq$  grade 1 within 3 weeks of holding study drug, axitinib should be permanently discontinued. Pembrolizumab therapy may be continued providing the residual adverse events are within permissible ranges for pembrolizumab dosing.

## 10.2 Dose Titration Guidelines for Axitinib

All patients will begin therapy at the starting dose level of 5 mg PO twice daily. Patients will be evaluated closely during cycle 1 for adverse events, laboratory studies, and review of study diaries and blood pressure logs. Additionally, patients will be instructed to call with any adverse events between study visits. **If there is no grade 2 or greater toxicity on cycle 2 day 1, the patient will be eligible for dose escalation of axitinib as per Table 8. Dose escalation DURING a cycle is not permitted. Consideration of escalation should only be done on day 1 of all subsequent cycles. If a patient is dose-escalated on day 1, they should resume blood pressure monitoring daily during the first three weeks of that cycle until evaluated during week 4 (i.e. day 22) visit of that same cycle.**

Dose reductions for grade 2 or greater toxicities may be done at any time during the cycles as per the following guidelines, and Tables 8 and 9.

- For grade 2 or greater fatigue, hand-foot syndrome, mucositis, or diarrhea, attempt medical supportive care first: (topical creams, anti-diarrheal, magic mouthwash or similar).
- If no improvement within 3 days, dose reduce axitinib as per Table 8.
- Axitinib may be held for 3-5 days prior to dose reduction in the judgment of the treating investigator, particularly for grade 3 toxicities

Management of Axitinib-related Hypertension:

- Patients will be provided with blood pressure cuffs and monitoring sheets. They will be instructed to monitor their blood pressure once daily before the evening dose of axitinib. They are to notify the study team for BP  $\geq$  150/100 mm Hg or for BP  $\geq$  120/80 mm Hg with any symptoms perceived to be related to BP (headache, chest pressure, shortness of breath, dizziness, blurry vision).
- Medications are to be added and titrated aggressively. Preferred sequence as follows:
  - Calcium channel blockers: (amlodipine, nifedipine, diltiazem, etc.)
  - ACE inhibitors or ARB (lisinopril, valsartan, losartan, etc.)
  - Diuretics (hydrochlorothiazide, furosemide). Patient should be prescribed concurrent potassium and magnesium supplementation and scheduled for potassium and magnesium laboratory tests within three days of starting.
  - Avoid beta-blockers, clonidine, digoxin.
  - If BP still  $\geq$  150/100 mm Hg despite maximal doses of three anti-hypertensive medications, axitinib should be reduced by one dose level.

Dose Level	Dose	If grade 2 or greater toxicity	If no grade 2 or greater toxicity after 21 days a
Dose reduction level -3	2 mg BID	Discontinue axitinib	Stay on 2mg BID c
Dose reduction level -2	3 mg BID	Dose reduce to 2mg BID b (can hold axitinib prior to restarting per MD discretion)	Stay on 3mg BID c
Dose reduction level -1	4 mg BID	Dose reduce to 3mg BID b (can hold axitinib prior to restarting per MD discretion)	Stay on 4mg BID c
Starting dose level	5 mg BID	Dose reduce to 4mg BIDb (can hold axitinib prior to restarting per MD discretion)	Dose escalate to 6 mg BID
Dose escalation level 1	6 mg BID	Dose reduce to 5mg BID b (can hold axitinib prior to restarting per MD discretion)	Dose escalate to 7 mg BID
Dose escalation level 2	7 mg BID	Dose reduce to 6mg BID b (can hold axitinib prior to restarting per MD discretion)	Dose escalate to 8 mg BID

Dose escalation level 3	8 mg BID	Dose reduce to 7mg BID b (can hold axitinib prior to restarting per MD discretion)	Dose escalate to 10 mg BID
Dose escalation level 4	10 mg BID	Dose reduce to 8mg BID b (can hold axitinib prior to restarting per MD discretion)	Maximal dose.

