**Table 10. Dose Titration of Axitinib**

a Dosing modifications based only on the following grade 2 toxicities: oral mucositis, diarrhea, hand-foot syndrome, fatigue. Dose modifications for other drug-related AEs as per table below and as per study principal investigator. CTC v4 definitions of grade 2 toxicities:

Oral mucositis: Moderate pain; not interfering with oral intake; modified diet indicated

Diarrhea: Increase of 4 - 6 stools per day over baseline

HFS: Skin changes (e.g., peeling, blisters, bleeding, edema, or hyperkeratosis) with pain; limiting instrumental ADL

Fatigue: Fatigue not relieved by rest; limiting instrumental ADL

b After dose reduction, re-escalation as tolerated may be considered per provider discretion

Toxicity	Grade:	Treatment	Dose reduction
Hypertension/ Hypertensive crisis  (Defined as $\geq$ 150/100 or symptoms such as headache, chest pressure, blurry vision)	2	Add appropriate anti-hypertensive medications	No dose reduction required
	3	Add appropriate anti-hypertensive medications	If persistent despite 3 or more medications and associated with persistent symptoms, dose reduce one level
	4	Discontinue axitinib	Discontinue axitinib
Thrombotic events (arterial)	2-4	Discontinue axitinib	Discontinue axitinib
Thrombotic events (venous) – uncomplicated DVT/PE	3	Provide anticoagulation	No dose adjustment required
Other venous thromboembolic disease (ie retinal vein occlusion)	3	Consider discontinuation of axitinib	Consider discontinuation of axitinib
Hemorrhage	2	Hold axitinib until resolution to $\leq$ grade 1	Dose reduce one dose level

	3	Hold axitinib until resolution to $\leq$ grade 1	Dose reduce one dose level. Discontinue if recurs with restarting medication.
	4	Discontinue axitinib.	Discontinue axitinib.
Thyroid dysfunction	2	Treat with replacement/suppression	No dose change
	3	Treat with replacement/suppression. Hold axitinib until resolution to $\leq$ grade 1. *refer to pembrolizumab dose modifications for additional treatment	Dose reduce one dose level
	4	Discontinue axitinib	Discontinue axitinib
Reversible posterior Leukoencephalopathy Syndrome	2-4	Discontinue axitinib	Discontinue axitinib

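### Section 10.2 and Table 10 differ on which toxicities block axitinib escalation, and on the better-supported reading no written rule bars escalation while hypertension is uncontrolled or symptomatic

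*Combined protocol and SAP*

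**What the plan says.** Section 10.2 sets the entry condition for escalation: "If there is no grade 2 or greater toxicity on cycle 2 day 1, the patient will be eligible for dose escalation of axitinib". The sentence does not limit the type of toxicity. It sends the reader to Table 8, an outdated number: the titration table is now Table 10. The current Table 8 is the pembrolizumab re-introduction schema, and the current Table 9 is the regimen description.

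In Table 10 the column that leads to a higher dose is headed "If no grade 2 or greater toxicity after 21 days" and carries footnote a. The footnote reads "Dosing modifications based only on the following grade 2 toxicities: oral mucositis, diarrhea, hand-foot syndrome, fatigue" and continues "Dose modifications for other drug-related AEs as per table below and as per study principal investigator". The table below it is Table 11, which has columns for treatment and for dose reduction and none for escalation. Table 11 takes hypertension as a pressure of at least "150/100 or symptoms such as headache, chest pressure, blurry vision". At grade 2 it asks for antihypertensive drugs and requires no reduction.

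The bullets in section 10.2 use the same four symptoms for reductions: "For grade 2 or greater fatigue, hand-foot syndrome, mucositis, or diarrhea, attempt medical supportive care first", then "If no improvement within 3 days, dose reduce axitinib as per Table 8".

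Other sections point to criteria without spelling them out. The synopsis (Study Design) makes escalation depend on the absence of predefined toxicities and cites section 7.1, Table 3 and section 10.2, Table 8. Section 7.0 uses the same phrase but cites only Table 3, which lists dose levels. Section 8.0 refers to specified criteria. Section 12.2.8 asks the investigator to consider escalation and refers back to section 10.2.

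**The concern.** Two places in the same section give different scopes for one dosing gate. The text counts every toxicity of grade 2 or above. The footnote counts four symptoms. Hypertension, a well-described axitinib effect, falls in the gap.

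Section 9.1.4 reports hypertension in 145 of 359 axitinib patients in the renal trial, with median onset within the first month. In the axitinib sarcoma trial cited in section 1.3, which according to section 1.4 did not escalate above 5 mg twice daily, grade 3/4 hypertension occurred in 7 of 60.

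What is at stake is higher exposure during an ongoing toxicity, and decisions that differ from patient to patient. Section 16.3 tabulates grade 3 and 4 toxicities by dose level but does not list grade 2 that way. Escalation during grade 2 hypertension might therefore not show in the planned safety tables.

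**Working it through.** The plan states no figure to reproduce here. The check is a comparison of rules for one patient, followed by a look at timing and numbers.

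**Rule comparison.** Take a patient on 5 mg twice daily, past the five-patient lead-in, with none of the four footnote symptoms. On cycle 2 day 1, blood pressure is still at or above 150/100 on one antihypertensive drug, at grade 2.

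| Source | Answer |
|---|---|
| Section 10.2 escalation sentence | Not eligible, since a grade 2 toxicity is present |
| Table 10, escalation column with footnote a | Column condition met; the entry is escalation to 6 mg twice daily |
| Footnote a, second sentence | Hypertension goes to Table 11 and the principal investigator |
| Table 11, hypertension grade 2 | Add drugs; no reduction; silent on escalation |
| Section 9.1.4 | Reduce the dose if hypertension persists despite drugs |

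**Which scope governs.** The escalation sentence itself defers to the table ("the patient will be eligible for dose escalation of axitinib as per Table 8"). The synopsis ties escalation to predefined toxicities in that same table. Table 3 contains dose levels only, so the one list of toxicities reached by the synopsis citation is footnote a. This favours footnote a, although no section says so outright and the table numbers that should connect the pieces are out of date.

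**What footnote a leaves open.** Some hypertensive patients are covered by another rule. Section 10.2 requires a reduction if pressure stays at or above 150/100 on maximal doses of three drugs. Table 11 reduces for grade 3 hypertension that persists with symptoms on three or more drugs, and discontinues at grade 4. The open cases are patients who are still at or above 150/100, or symptomatic, without meeting those triggers. For them the tables give no bar, only discretion.

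**Timing.** Cycle 1 lasts 7 × 7 = 49 days, so cycle 2 day 1 is day 50. A median onset within the first month puts about half of the hypertension cases, if the renal pattern applies, before the first escalation decision.

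**Numbers.** The documents do not say how many patients are uncontrolled or symptomatic on day 1. Applying the renal all-grade rate, as an assumption, to the 40 − 5 = 35 patients after the lead-in gives 35 × 145/359 = 14.1; to 10 expansion patients, 10 × 145/359 = 4.0. These are too high for a day 1 count: the rate covers all grades and the whole treatment period, and includes patients controlled by day 1. The floor is 0. A range of 0 to 14 of 35 is not an estimate.

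**Decisions still to come.** The expansion was added in version 4.0 (March 2018). At one patient every two months, ten patients take 10 × 2 = 20 months, to about November 2019. Version 7.0 is dated April 2020. Actual accrual is not given, so cycle 2 day 1 decisions may already be over. Sections 8.0 and 12.2.16 still allow escalation on day 1 of later cycles.

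**The case against.** The strongest reply is that there is one rule, loosely drafted. The escalation sentence defers to the table, the table heading repeats the sentence's condition, footnote a sits on the escalation column, and the synopsis points to the same table. Other events go to the principal investigator of a single-institution trial, and escalation is only to be considered. Daily blood pressure logs, weekly cycle 1 visits and aggressive use of antihypertensives make uncontrolled pressure on day 50 less likely.

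Most of this stands, and it rules out several stronger readings that a reader might infer:

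- *The text is a blanket bar that the tables override.* The synopsis favours footnote a as the list. The four symptoms also appear in the reduction bullets, but that does not remove a footnote marked on the escalation column.
- *The tables tell the investigator to escalate hypertensive patients.* They leave the matter to the principal investigator.
- *The text and tables conflict at every cycle.* The any-toxicity sentence is limited to cycle 2 day 1.
- *Hypertension controlled before day 1 is also in conflict.* A patient below 150/100 and without symptoms does not meet the Table 11 definition that day.

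The reply does not close the gap. If footnote a governs, the only sentence that would have stopped escalation in a patient at or above 150/100 no longer does so, and Table 11 puts nothing in its place. Discretion is not a written limit.

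**Conclusion.** The point holds in a limited form. The section 10.2 text and Table 10 give different scopes for the cycle 2 day 1 gate. The better-supported scope, footnote a, leaves escalation unbarred while hypertension is uncontrolled or symptomatic, against the direction of section 9.1.4. This is a patient-safety correction to a dosing rule and should be made.

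The number affected cannot be estimated from the documents and may be small if accrual is complete. Nothing in the documents shows that any patient was in fact escalated while hypertensive. The primary endpoint, power and alpha are not touched. The conclusion rests on taking the synopsis citation of Table 8 to mean the current Table 10, and on Table 11 being the only written rule for hypertension apart from the three-drug reduction bullet and section 9.1.4.

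**What to change.** 1. State in section 10.2 and in Table 11 that axitinib is not escalated on day 1 of any cycle while blood pressure is at or above 150/100 or hypertension is symptomatic.
2. State in section 10.2 that the footnote a list otherwise governs escalation, and that any other ongoing drug-related toxicity of grade 2 or above needs a documented principal investigator decision before the dose is raised. This should not be a blanket bar. Table 11 makes no dose change for grade 2 thyroid dysfunction and needs no adjustment for grade 3 uncomplicated DVT or PE under anticoagulation, and section 7.1 aims to maximize exposure. Such patients should not be excluded automatically.
3. Correct the section 10.2 references from Tables 8 and 9 to Tables 10 and 11.

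The cost is a wording amendment, a line of documentation for each principal investigator decision, and later escalation for some patients. Sample size and the efficacy analysis do not change.
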